7.5. Electrocardiogram Results

Electrocardiogram (ECG) data will not be presented in the CSR since ECGs were not assessed in this study other than as part of the screening process for potential new subjects.

7.6. Other Safety Measures

7.6.1. Stool Frequency

Stool frequency subscore from the partial Mayo Score will be summarized by visit and treatment group. Change from baseline will be summarized in the following 3 ordered categories: increased, no change, and decreased. A baseline value in the Randomized/OL Phase will be defined as the last available value collected on or prior to the date/time of first dose of study drug in the corresponding treatment phase.

Table 7-1. Stool Frequency Subscore of Partial Mayo Score

Domain	Description	Score
Stool Frequency (based on the past 3 days)	Normal number of stools	0
	1-2 stools more than normal	1
	3-4 stools more than normal	2
	5 or more stools more than normal	3

7.7. Changes From Protocol-Specified Safety Analyses

There are no deviations from the protocol-specified safety analyses in this SAP.

8. PHARMACOKINETIC ANALYSES

A single PK blood sample will be collected during the Randomized Phase at Week 1, 4, 12, 24, and 48 visits in all subjects and during the OL Phase at all visits only in subjects with severe hepatic impairment (Child-Pugh Class C) in combination with renal impairment (eGFR < 30 mL/min)

CCI

Concentrations of SEL and GS-607509 in plasma will be determined using validated bioanalytical assays. A population PK model will be developed to characterize the PK of SEL and its metabolite (as applicable). Data from this study (single PK and PK substudy) will be combined with data from other studies in a meta-population analysis using nonlinear mixed-effects modeling techniques. Details of the population PK analysis will be provided in a separate population PK analysis report.

The following listing will be provided for both single and intensive PK samples:

- PK sampling details by subject and analyte including actual dosing time and actual draw time, calculated time postdose of sample collection, differences in scheduled and actual draw times, sample age, and sample concentration

10. SOFTWARE

SAS[®] Software Version 9.4. SAS Institute Inc., Cary, NC, USA.

nQuery +nTerim Version 4.0. Statistical Solutions, Cork, Ireland.

EAST Version 6. Cytel. Cambridge, MA, USA.

11. SAP REVISION

Revision Date (DD MMM YYYY)	Section	Summary of Revision	Reason for Revision

12. APPENDICES

- Appendix 1. Study Procedures Table – Screening to Week 48
- Appendix 2. CTCAE Grade for Laboratory Parameters
- Appendix 3. Pooled Cohort Risk and Score Calculation
- Appendix 4. Liver Function Prognostic Scores
- Appendix 5. Health Related QoL Score Calculation
- Appendix 6. NAFLD Activity Score (NAS) and Steatosis, Activity, and Fibrosis (SAF) Score Calculation
- Appendix 7. Noninvasive markers for Fibrosis
- Appendix 8. SAS Program for Tipping Point Analysis for Binary Endpoint

Appendix 1. Study Procedures Table – Screening to Week 48

Assessments	Screening	Day 1 ^a	On-treatment Visits												
			Week 1	Week 4	Week 8	Week 12	Week 16	Week 20	Week 24	Week 28	Week 32	Week 36	Week 40	Week 44	Week 48
Clinical Assessments															
Written Informed Consent	X														
Determine Eligibility	X														
Medical History	X														
Physical Examination	X	X ^b	X ^b	X ^b	X ^b	X ^b	X ^b	X ^b	X ^b	X ^b	X ^b	X ^b	X ^b	X ^b	X ^b
Vital Signs including Body Weight	X	X	X	X	X	X	X	X	X	X	X	X	X	X	X
Height	X														
Waist Circumference	X	X		X		X			X						X
12-lead ECG	X														
CP/MELD Scores ^c	X	X	X	X	X	X	X	X	X	X	X	X	X	X	X
Assess Ascites and Hepatic Encephalopathy	X	X	X	X	X	X	X	X	X	X	X	X	X	X	X
Liver Biopsy ^d	X														X
Abdominal Ultrasound (OL Phase only)		X							X						X
Elastography (if available)	X ^e	X ^f							X						X

Assessments	Screening	Day 1 ^a	On-treatment Visits												
			Week 1	Week 4	Week 8	Week 12	Week 16	Week 20	Week 24	Week 28	Week 32	Week 36	Week 40	Week 44	Week 48
Health Related Quality of Life Questionnaires ^g		X				X			X						X
Health Resource Utilization Questionnaires ^g		X				X			X						X
Stool Frequency Assessment		X	X	X	X	X	X	X	X	X	X	X	X	X	X
Lifestyle Modification Counseling		X	X	X	X	X	X	X	X	X	X	X	X	X	X
Adverse Events	X ^h	X	X	X	X	X	X	X	X	X	X	X	X	X	X
Concomitant Medications	X	X	X	X	X	X	X	X	X	X	X	X	X	X	X
Dispense Study Drug		X		X	X	X	X	X	X	X	X	X	X	X	X
Review of Study Drug Dosing Compliance (Pill Count)			X	X	X	X	X	X	X	X	X	X	X	X	X
Laboratory Assessments															
Subject Fasting	X	X	X	X	X	X	X	X	X	X	X	X	X	X	X
Chemistry ⁱ , Hematology, Coagulation	X	X	X	X	X	X	X	X	X	X	X	X	X	X	X
Insulin and Lipids		X		X		X			X						X
HbA1c	X	X		X		X			X						X
eGFR	X	X	X	X	X	X	X	X	X	X	X	X	X	X	X
Pregnancy Testing ^j	X	X		X	X	X	X	X	X	X	X	X	X	X	X

Assessments	Screening	Day 1 ^a	On-treatment Visits												
			Week 1	Week 4	Week 8	Week 12	Week 16	Week 20	Week 24	Week 28	Week 32	Week 36	Week 40	Week 44	Week 48
Single PK Sampling		X ^l	X ^k	X ^k	X ^l	X ^k	X ^l	X ^l	X ^k	X ^l	X ^l	X ^l	X ^l	X ^l	X ^k
Blood Collection (Biomarkers)	X	X				X			X						X
Urine Collection		X				X			X						X
Urine Drug Screen	X														
HIV-1, HBV, HCV Serology	X														
CCI CCI															
Approximate amount of blood drawn (mL) ⁿ	70	65	15	15	12	60	12	12	60	12	12	12	12	12	65

Study Procedures Table – Week 60 to Follow Up

Assessments	On-treatment Visits										Follow Up ^o	Telephone Follow-Up ^p
	Week 60	Week 72	Week 84	Week 96	Week 108	Week 120	Week 132	Week 144	Week 156	ET ^o		
		Week 168	Week 180	Week 192	Week 204	Week 216	Week 228	Week 240 (EOT)				
Physical Examination	X ^b	X ^b	X ^b	X ^b	X ^b	X ^b	X ^b	X ^b	X ^b	X ^b	X ^b	
Vital Signs including Body Weight	X	X	X	X	X	X	X	X	X	X	X	
Waist Circumference		X		X		X		X		X		
Liver Biopsy ^d								X ^q		X ^r		
CP/MELD scores ^e	X	X	X	X	X	X	X	X	X	X		
Assess Ascites and Hepatic Encephalopathy	X	X	X	X	X	X	X	X	X	X		
Abdominal Ultrasound (OL Phase only)		X		X		X		X		X		
Elastography (if available)				X				X		X		
Health Related Quality of Life Questionnaires ^g		X		X		X		X		X		
Health Resource Utilization Questionnaires ^g		X		X		X		X		X		
Stool Frequency Assessment	X	X	X	X	X	X	X	X	X	X	X	
Lifestyle Modification Counseling	X	X	X	X	X	X	X	X	X	X		
Adverse Events	X	X	X	X	X	X	X	X	X	X	X	X
Concomitant Medications	X	X	X	X	X	X	X	X	X	X	X	
Dispense Study Drug	X	X	X	X	X	X	X	X ^s	X			
Review of Study Drug Dosing Compliance (Pill Count)	X	X	X	X	X	X	X	X	X	X		

Assessments	On-treatment Visits										Follow Up ^o	Telephone Follow-Up ^p
	Week 60	Week 72	Week 84	Week 96	Week 108	Week 120	Week 132	Week 144	Week 156	ET ^o		
		Week 168	Week 180	Week 192	Week 204	Week 216	Week 228	Week 240 (EOT)				
Laboratory Assessments												
Subject Fasting	X	X	X	X	X	X	X	X	X	X	X	
Chemistry ⁱ , Hematology, Coagulation	X	X	X	X	X	X	X	X	X	X	X	
Insulin and Lipids		X		X		X		X		X		
HbA1c		X		X		X		X		X		
eGFR	X	X	X	X	X	X	X	X	X	X	X	
Pregnancy Testing ^j	X	X	X	X	X	X	X	X	X	X	X	
Single PK sampling ^l	X	X	X	X	X	X	X	X	X	X ⁱ		
Blood Collection (Biomarkers)				X				X		X		
Urine Collection				X				X		X		
CCI												
Approximate amount of blood drawn (mL) ⁿ	12	15	12	65	12	15	12	65	12	65	10	

- a Subjects starting the OL Phase of the study will complete the same study procedures as during the Randomized Phase of the study, starting with the Day 1 visit
- b Symptom-driven PE
- c CP score to be calculated only at Screening
- d Not to be performed during the OL Phase of the study
- e CCI
- f CCI
- g For subjects with questionnaires available at Day 1
- h Adverse Events reporting during Screening is limited to serious adverse events and adverse events related to study procedures
- i Additional testing: digoxin level at Day 1 and Week 1 and as needed in subjects taking digoxin (refer to Section 5.4 of the protocol) and CPK level for subjects in close observation for DILI (refer to Section 7.5 of the protocol)

- j Females of childbearing potential only (refer to Appendix 3 of the protocol). Serum pregnancy test at Screening and urine pregnancy test at Day 1 and every 4 weeks thereafter. Starting at the Week 48 visit, urine pregnancy testing kits will be provided for home testing every 4 weeks, between in-clinic study visits. All females of childbearing potential will be contacted every 4 weeks and asked to report the result of the urine pregnancy tests. FSH testing as per Appendix 3 of the protocol
- k To be performed during the Randomized Phase in all subjects and during the OL Phase, only in subjects with severe hepatic impairment (Child-Pugh Class C) in combination with renal impairment (eGFR < 30 mL/min)
- l To be performed during the OL Phase, only in subjects with severe hepatic impairment (Child-Pugh Class C) in combination with renal impairment (eGFR < 30 mL/min)
- m **CCI**
- n For specific blood volumes at each visit, please refer to the current approved ICF
- o Subjects prematurely discontinuing from the study should complete an ET visit within 30 days of last dose, Follow-Up visit 4 weeks later and a Telephone Follow-Up visit after the ET visit
- p To be performed 12 weeks after the Week 240/EOT or ET visit. At the discretion of the investigator, an unscheduled visit may be completed if the subject reports abnormal or concerning symptoms
- q Not to be performed at the Week 144 visit
- r To be performed at the discretion of the investigator
- s Not to be performed at the Week 240/EOT visits
- t To be collected in all subjects that ET in Randomized or OL Phase

Appendix 2. CTCAE Grade for Laboratory Parameters

CTCAE 5.0	CTCAE Grade				
CTCAE Term	Grade 1	Grade 2	Grade 3	Grade 4	Grade 5
Anemia	Hemoglobin (Hgb) <LLN - 10.0 g/dL; <LLN - 6.2 mmol/L; <LLN - 100 g/L	Hgb <10.0 - 8.0 g/dL; <6.2 - 4.9 mmol/L; <100 - 80g/L	Hgb <8.0 g/dL; <4.9 mmol/L; <80 g/L; transfusion indicated	Life-threatening consequences; urgent intervention indicated	Death
Activated partial thromboplastin time prolonged	>ULN - 1.5 x ULN	>1.5 - 2.5 x ULN	>2.5 x ULN; bleeding	-	-
Alanine aminotransferase increased	>ULN - 3.0 x ULN if baseline was normal; 1.5 - 3.0 x baseline if baseline was abnormal	>3.0 - 5.0 x ULN if baseline was normal; >3.0 - 5.0 x baseline if baseline was abnormal	>5.0 - 20.0 x ULN if baseline was normal; >5.0 - 20.0 x baseline if baseline was abnormal	>20.0 x ULN if baseline was normal; >20.0 x baseline if baseline was abnormal	-
Alkaline phosphatase increased	>ULN - 2.5 x ULN if baseline was normal; 2.0 - 2.5 x baseline if baseline was abnormal	>2.5 - 5.0 x ULN if baseline was normal; >2.5 - 5.0 x baseline if baseline was abnormal	>5.0 - 20.0 x ULN if baseline was normal; >5.0 - 20.0 x baseline if baseline was abnormal	>20.0 x ULN if baseline was normal; >20.0 x baseline if baseline was abnormal	-
Aspartate aminotransferase increased	>ULN - 3.0 x ULN if baseline was normal; 1.5 - 3.0 x baseline if baseline was abnormal	>3.0 - 5.0 x ULN if baseline was normal; >3.0 - 5.0 x baseline if baseline was abnormal	>5.0 - 20.0 x ULN if baseline was normal; >5.0 - 20.0 x baseline if baseline was abnormal	>20.0 x ULN if baseline was normal; >20.0 x baseline if baseline was abnormal	-
Blood bicarbonate decreased	<LLN and no intervention initiated	-	-	-	-
Blood bilirubin increased	>ULN - 1.5 x ULN if baseline was normal; > 1.0 - 1.5 x baseline if baseline was abnormal	>1.5 - 3.0 x ULN if baseline was normal; >1.5 - 3.0 x baseline if baseline was abnormal	>3.0 - 10.0 x ULN if baseline was normal; >3.0 - 10.0 x baseline if baseline was abnormal	>10.0 x ULN if baseline was normal; >10.0 x baseline if baseline was abnormal	-
Cholesterol high	>ULN - 300 mg/dL; >ULN - 7.75 mmol/L	>300 - 400 mg/dL; >7.75 - 10.34 mmol/L	>400 - 500 mg/dL; >10.34 - 12.92 mmol/L	>500 mg/dL; >12.92 mmol/L	-
CPK increased	>ULN - 2.5 x ULN	>2.5 x ULN - 5 x ULN	>5 x ULN - 10 x ULN	>10 x ULN	-

CTCAE 5.0	CTCAE Grade				
CTCAE Term	Grade 1	Grade 2	Grade 3	Grade 4	Grade 5
Creatinine increased	>ULN - 1.5 x ULN	>1.5 - 3.0 x baseline; >1.5 - 3.0 x ULN	>3.0 x baseline; >3.0 - 6.0 x ULN	>6.0 x ULN	-
GGT increased	>ULN - 2.5 x ULN if baseline was normal; 2.0 - 2.5 x baseline if baseline was abnormal	>2.5 - 5.0 x ULN if baseline was normal; >2.5 - 5.0 x baseline if baseline was abnormal	>5.0 - 20.0 x ULN if baseline was normal; >5.0 - 20.0 x baseline if baseline was abnormal	>20.0 x ULN if baseline was normal; >20.0 x baseline if baseline was abnormal	-
Haptoglobin decreased	<LLN	-	-	-	-
Hemoglobin increased	Increase in >0 - 2 g/dL	Increase in >2 - 4 g/dL	Increase in >4 g/dL	-	-
INR increased	>1.2 - 1.5; >1 - 1.5 x baseline if on anticoagulation; monitoring only indicated	>1.5 - 2.5; >1.5 - 2.5 x baseline if on anticoagulation; dose adjustment indicated	>2.5; >2.5 x baseline if on anticoagulation; bleeding	-	-
Lipase increased	>ULN - 1.5 x ULN	>1.5 - 2.0 x ULN; >2.0 - 5.0 x ULN and asymptomatic	>2.0 - 5.0 x ULN with signs or symptoms; >5.0 x ULN and asymptomatic	>5.0 x ULN and with signs or symptoms	-
Lymphocyte count decreased	<LLN - 800/mm ³ ; <LLN - 0.8 x 10 ⁹ /L	<800 - 500/mm ³ ; <0.8 - 0.5 x 10 ⁹ /L	<500 - 200/mm ³ ; <0.5 - 0.2 x 10 ⁹ /L	<200/mm ³ ; <0.2 x 10 ⁹ /L	-
Lymphocyte count increased	-	>4000/mm ³ - 20,000/mm ³	>20,000/mm ³	-	-
Neutrophil count decreased	<LLN - 1500/mm ³ ; <LLN - 1.5 x 10 ⁹ /L	<1500 - 1000/mm ³ ; <1.5 - 1.0 x 10 ⁹ /L	<1000 - 500/mm ³ ; <1.0 - 0.5 x 10 ⁹ /L	<500/mm ³ ; <0.5 x 10 ⁹ /L	-
Platelet count decreased	<LLN - 75,000/mm ³ ; <LLN - 75.0 x 10 ⁹ /L	<75,000 - 50,000/mm ³ ; <75.0 - 50.0 x 10 ⁹ /L	<50,000 - 25,000/mm ³ ; <50.0 - 25.0 x 10 ⁹ /L	<25,000/mm ³ ; <25.0 x 10 ⁹ /L	-
Serum amylase increased	>ULN - 1.5 x ULN	>1.5 - 2.0 x ULN; >2.0 - 5.0 x ULN and asymptomatic	>2.0 - 5.0 x ULN with signs or symptoms; >5.0 x ULN and asymptomatic	>5.0 x ULN and with signs or symptoms	-
White blood cell decreased	<LLN - 3000/mm ³ ; <LLN - 3.0 x 10 ⁹ /L	<3000 - 2000/mm ³ ; <3.0 - 2.0 x 10 ⁹ /L	<2000 - 1000/mm ³ ; <2.0 - 1.0 x 10 ⁹ /L	<1000/mm ³ ; <1.0 x 10 ⁹ /L	-

CTCAE 5.0	CTCAE Grade				
CTCAE Term	Grade 1	Grade 2	Grade 3	Grade 4	Grade 5
Hypercalcemia	Corrected serum calcium of >ULN - 11.5 mg/dL; >ULN - 2.9 mmol/L; Ionized calcium >ULN - 1.5 mmol/L	Corrected serum calcium of >11.5 - 12.5 mg/dL; >2.9 - 3.1 mmol/L; Ionized calcium >1.5 - 1.6 mmol/L; symptomatic	Corrected serum calcium of >12.5 - 13.5 mg/dL; >3.1 - 3.4 mmol/L; Ionized calcium >1.6 - 1.8 mmol/L; hospitalization indicated	Corrected serum calcium of >13.5 mg/dL; >3.4 mmol/L; Ionized calcium >1.8 mmol/L; life-threatening consequences	Death
Hyperkalemia	>ULN - 5.5 mmol/L	>5.5 - 6.0 mmol/L; intervention initiated	>6.0 - 7.0 mmol/L; hospitalization indicated	>7.0 mmol/L; life-threatening consequences	Death
Hypermagnesemia	>ULN - 3.0 mg/dL; >ULN - 1.23 mmol/L	-	>3.0 - 8.0 mg/dL; >1.23 - 3.30 mmol/L	>8.0 mg/dL; >3.30 mmol/L; life-threatening consequences	Death
Hypernatremia	>ULN - 150 mmol/L	>150 - 155 mmol/L; intervention initiated	>155 - 160 mmol/L; hospitalization indicated	>160 mmol/L; life-threatening consequences	Death
Hypertriglyceridemia	150 mg/dL - 300 mg/dL; 1.71 mmol/L - 3.42 mmol/L	>300 mg/dL - 500 mg/dL; >3.42 mmol/L - 5.7 mmol/L	>500 mg/dL - 1000 mg/dL; >5.7 mmol/L - 11.4 mmol/L	>1000 mg/dL; >11.4 mmol/L; life-threatening consequences	Death
Hyperuricemia	>ULN without physiologic consequences	-	>ULN with physiologic consequences	Life-threatening consequences	Death
Hypoalbuminemia	<LLN - 3 g/dL; <LLN - 30 g/L	<3 - 2 g/dL; <30 - 20 g/L	<2 g/dL; <20 g/L	Life-threatening consequences; urgent intervention indicated	Death
Hypocalcemia	Corrected serum calcium of <LLN - 8.0 mg/dL; <LLN - 2.0 mmol/L; Ionized calcium <LLN - 1.0 mmol/L	Corrected serum calcium of <8.0 - 7.0 mg/dL; <2.0 - 1.75 mmol/L; Ionized calcium <1.0 - 0.9 mmol/L; symptomatic	Corrected serum calcium of <7.0 - 6.0 mg/dL; <1.75 - 1.5 mmol/L; Ionized calcium <0.9 - 0.8 mmol/L; hospitalization indicated	Corrected serum calcium of <6.0 mg/dL; <1.5 mmol/L; Ionized calcium <0.8 mmol/L; life-threatening consequences	Death

CTCAE 5.0	CTCAE Grade				
CTCAE Term	Grade 1	Grade 2	Grade 3	Grade 4	Grade 5
Hypoglycemia	<LLN - 55 mg/dL; <LLN - 3.0 mmol/L	<55 - 40 mg/dL; <3.0 - 2.2 mmol/L	<40 - 30 mg/dL; <2.2 - 1.7 mmol/L	<30 mg/dL; <1.7 mmol/L; life-threatening consequences; seizures	Death
Hypokalemia	<LLN - 3.0 mmol/L	Symptomatic with <LLN - 3.0 mmol/L; intervention indicated	<3.0 - 2.5 mmol/L; hospitalization indicated	<2.5 mmol/L; life-threatening consequences	Death
Hypomagnesemia	<LLN - 1.2 mg/dL; <LLN - 0.5 mmol/L	<1.2 - 0.9 mg/dL; <0.5 - 0.4 mmol/L	<0.9 - 0.7 mg/dL; <0.4 - 0.3 mmol/L	<0.7 mg/dL; <0.3 mmol/L; life-threatening consequences	Death
Hyponatremia	<LLN - 130 mmol/L	125-129 mmol/L and asymptomatic	125-129 mmol/L symptomatic; 120-124 mmol/L regardless of symptoms	<120 mmol/L; life-threatening consequences	Death

* Since anticoagulation medication is **NOT** captured in lab data, the condition for anticoagulation medication is ignored in the grade derivation.

a Note: Refer to Common Terminology Criteria for Adverse Events (CTCAE) Version 5.0, which can be found at https://evs.nci.nih.gov/ftp1/CTCAE/CTCAE_5.0

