### **5.4. Prior and Concomitant Medications**

All concomitant medication will be recorded in the source documents and eCRFs. This includes concomitant medications taken within 30 days prior to Screening and any taken during the study to the end of the follow-up period.

The following medications are prohibited for all treatment groups:

- Any investigational medication or device within 30 days or within 5 half-lives of the prior investigational agent (whichever is longer) prior to Screening and throughout the study. Subjects enrolled in the current protocol may participate concurrently in a HepQuantTM sponsored investigational device study at participating US sites only (Investigational Device Exemption # G170034/S001), once approved by the applicable IRB/IEC.
- Strong cytochrome P4503A4 (CYP3A4) inducers may decrease the exposure of SEL and could lead to decreased efficacy. Use of strong CYP3A4 inducers is prohibited from 2 weeks prior to Day 1 through end of treatment.

Caution should be exercised when co-administering sensitive P-gp substrates with narrow therapeutic index with SEL as it may increase the concentrations of these agents. The investigator should review the prescribing information of the concomitant medication for guidance on co-administration with a weak P-gp inhibitor.

Subjects on Vitamin E must be on a stable dose for at least 6 months prior to the diagnostic liver biopsy and subjects on antidiabetic medication(s) must be on stable dose(s) for at least 3 months prior to the diagnostic liver biopsy. If possible, the doses of these medications should remain stable through the End of Treatment.

Examples of representative medications that are prohibited from 2 weeks prior to Day 1 as well as specific medications which are prohibited or which should be used with caution from 30 days prior to Day 1 are listed below in [Table 5-1](#).

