7.2.3. Liver-related Laboratory Evaluations

The summary will be provided by 3 subgroups of subjects according to their baseline ALT/AST level in the Randomized/OL Phase:

- Normal
- Elevated (> 1 to $< 5 \times$ upper limit of normal [ULN])
- Elevated ($\geq 5 \times$ ULN)

Liver-related abnormalities after initial study drug dosing will be examined and summarized using the number and percentage of subjects who were reported to have the following laboratory test values for postbaseline measurements:

For subjects with normal baseline ALT/AST:

- Subjects meeting criteria for close observation
 - $ALT/AST > 3 \times ULN$
- Subjects meeting criteria for holding study drug
 - $ALT/AST > 8 \times ULN$
 - $ALT/AST > 5 \times ULN$ for 2 weeks
 - $ALT/AST > 3 \times ULN$ and total bilirubin $> 2 \times ULN$ (or direct bilirubin $2 \times$ baseline in subjects with Gilbert's syndrome)
 - $ALT/AST > 3 \times ULN$ and $INR > 1.5$ (if not on anticoagulation)

For subjects with baseline ALT/AST between 1 and $5 \times ULN$

- Subjects meeting criteria for close observation
 - $ALT/AST > 2 \times$ Baseline or > 300 U/L
- Subjects meeting criteria for holding study drug
 - $ALT/AST > 8 \times$ Baseline or > 500 U/L
 - $ALT/AST > 3 \times$ Baseline or > 300 U/L, and total bilirubin $> 2 \times ULN$ (or direct bilirubin $2 \times$ Baseline in subjects with Gilbert's syndrome)
 - $ALT/AST > 3 \times$ Baseline and $INR > 1.5$ (if not on anticoagulation)

For subjects with baseline $ALT/AST \geq 5 \times ULN$

- Subjects meeting criteria for close observation
 - $ALT/AST > 2 \times$ Baseline
- Subjects meeting criteria for holding study drug
 - $ALT/AST > 500$ U/L

The above summary will include data from all postbaseline visits up to 30 days after the last dose of study drug for subjects who permanently discontinued study drug (and before OL Study Day 1 for abnormalities in the Randomized Phase) in the reporting phase, or the last available date in the database snapshot for subjects who were still on treatment at the time of an interim analysis. The denominator is the number of subjects in the (OL) Safety Analysis Set who have nonmissing

postbaseline values of all relevant tests at the same postbaseline visit date in the summarizing group. A listing of subjects meeting any of the criteria above will be provided.

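### INR toxicity grades ignore anticoagulation, although that status is recorded and SAP 7.2.3 already needs it, so therapeutic INRs can appear as treatment-emergent Grade 2-3 abnormalities

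*SAP*

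**What the plan says.** SAP 7.2.2 grades laboratory results by CTCAE Version 5.0, using the table in Appendix 2. The INR row carries two limits at each grade, one absolute and one relative to baseline for anticoagulated subjects. Grade 2 reads ">1.5 - 2.5; >1.5 - 2.5 x baseline if on anticoagulation; dose adjustment indicated". Grade 3, the highest INR grade, reads ">2.5; >2.5 x baseline if on anticoagulation; bleeding". A footnote then says that anticoagulant use is not held in the laboratory data and that "the condition for anticoagulation medication is ignored in the grade derivation". INR is the only row with such a condition, so the absolute limits apply to everyone.

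Four other places bear on this:

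- Protocol 5.4: "All concomitant medication will be recorded in the source documents and eCRFs". SAP 7.4 codes these records in the WHO Drug dictionary.
- SAP 7.2.3: the liver criteria that combine raised ALT/AST with INR above 1.5 apply only "if not on anticoagulation".
- SAP Appendix 3: treated or untreated blood pressure is decided by matching dated antihypertensive records to the date of measurement.
- Protocol 4.2 and 4.3: the INR limit of 1.4 and the Child-Pugh and MELD limits are waived when therapeutic anticoagulation is the cause, so such subjects can be enrolled.

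On counting, SAP 7.2.2.1 calls a value treatment-emergent when it is at least one grade above baseline, and 7.2.2.2 calls it marked when it is at least three grades above.

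**The concern.** The SAP treats anticoagulant status as unavailable in one INR analysis and as available in another. The status can be derived, and the SAP already does the same kind of linkage for antihypertensives.

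INR is a synthetic-function test in a liver-disease trial, and an entry in its Grade 3 row will be read as a safety finding. If therapeutic INRs enter that row, the absolute rates are inflated in every arm and a reader cannot tell a drug or disease effect from intended anticoagulation without going to the listings.

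**Working it through.** The plan states no figure on this point, so there is nothing to reproduce. The check applies the two printed rules to example values and then sizes the effect under stated assumptions.

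**Step 1. The rules applied to single subjects.** With the footnote: INR above 1.2 to 1.5 is Grade 1, above 1.5 to 2.5 is Grade 2, above 2.5 is Grade 3. With the printed anticoagulation limits: above 1 to 1.5 x baseline is Grade 1, above 1.5 to 2.5 x is Grade 2, above 2.5 x is Grade 3.

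| Baseline to post-baseline INR | Footnote: baseline to post grade | Counted as treatment-emergent? | Ratio to baseline | Grade by printed limits |
|---|---|---|---|---|
| 2.4 to 2.6 | 2 to 3 | Yes, Grade 3 | 1.08 | 1 |
| 2.2 to 2.6 | 2 to 3 | Yes, Grade 3 | 1.18 | 1 |
| 2.5 to 3.0 | 2 to 3 | Yes, Grade 3 | 1.20 | 1 |
| 2.0 to 2.4 | 2 to 2 | No | 1.20 | 1 |
| 2.6 to 3.0 | 3 to 3 | No | 1.15 | 1 |
| 1.0 to 2.3 (new starter) | 0 to 2 | Yes, Grade 2 | 2.30 | 2 |
| 1.0 to 2.6 (new starter) | 0 to 3 | Yes, Grade 3 and marked | 2.60 | 3 |

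Stable users are counted mainly when they cross 2.5 from below. New starters are counted under either rule.

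**Step 2. Share of stable users counted.** The number of visits comes from the schedule: 13 post-baseline visits to Week 48 (Weeks 1, 4 and then every 4 weeks) plus (240 - 48)/12 = 16 more, giving 29. Assumptions not in the documents: INR normal with mean 2.2 to 2.5 and SD 0.4, independent across visits, all visits attended. A treatment-emergent Grade 3 needs a baseline at or below 2.5 and at least one later value above it. With p = Phi((2.5 - mean)/0.4), the probability is p - p^30.

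- Mean 2.2: p = Phi(0.75) = 0.773; 0.773^30 is below 0.001; result about 77%.
- Mean 2.5: p = 0.5; 0.5^30 is negligible; result about 50%.

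A simulation with mean 2.5, SD 0.3 to 0.7, 13 or 29 visits and INR rounded to one decimal gives 53-57%. This is slightly above 50% because a value that rounds to 2.5 stays in Grade 2.

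**Step 3. Number of subjects.** Assume 2-5% of 800 take an INR-raising anticoagulant: 16 to 40 subjects. Then 16 x 0.50 = 8 and 40 x 0.773 = 31. Per arm this is 3.2 to 12.4 of 320 on each SEL dose and 1.6 to 6.2 of 160 on placebo, or 1.0% to 3.9% of each arm.

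**Step 4. After applying the printed limits to stable users.** In the same simulation, Grade 3 falls to about 0-9% (0-1.5% at SD 0.3 and 0.5). The highest grade becomes Grade 2 in about 5-46% and Grade 1 in about 41-87%. The Grade 1 entries follow from the rule itself: any value above baseline qualifies, and with 29 exchangeable values the chance of at least one is 29/30 = 97%.

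**The case against.** The strongest reply is that the liver-safety assessment does not rest on these grades. SAP 7.2.3 already excludes anticoagulated subjects from its INR criteria, and SAP 7.2.4 finds potential DILI cases from 7.2.3, not from CTCAE grades. The simplification is disclosed. The SAP also lists all results for any test with a treatment-emergent Grade 3 or 4 value, and lists all concomitant medication by subject, so individual cases can be traced. Randomisation should roughly balance anticoagulant use across arms.

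Most of this stands and limits the point to the general graded tables and listing. It does not remove the point. Every INR criterion in 7.2.3 also requires raised ALT or AST, and the group with baseline ALT/AST at or above 5 x ULN has no INR criterion. An INR rise without an ALT/AST rise is therefore graded only in the tables that the footnote affects. Balance between arms does not correct inflated absolute rates.

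A second reply also stands: the printed limits do not help a new starter. An INR of 2.6 from a baseline of 1.0 is 2.6 x baseline, which is still Grade 3 and marked. The separate display on and off anticoagulation is therefore the essential part of the fix.

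A reader might also infer that nearly every user becomes a false Grade 3, since the chance of at least one of 29 values above 2.5 is 1 - 0.773^29 = 0.9994 even at a mean of 2.2. The counting rule does not support this: a subject whose baseline is already Grade 3 cannot be treatment-emergent.

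**Conclusion.** The inconsistency is real, and the stated reason for ignoring anticoagulation does not justify it. Therapeutic INRs can create false treatment-emergent Grade 2-3 entries in the graded and Grade 3-4 laboratory tables.

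The size is unknown because the documents give no anticoagulant prevalence and no INR distribution. Under the assumptions in the working, it is roughly 8-31 of 800 subjects from stable users, with on-study starters in addition and not estimated.

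Three stronger readings are not supported. First, nothing shows that false entries would hide or mimic a drug effect: prevalence is unknown, use should be similar across arms, and the liver criteria and DILI case-finding are separate. Second, stable users would rarely be marked. That requires a baseline INR of 1.2 or less, with probability Phi((1.2 - 2.2)/0.4) = Phi(-2.5) = 0.6% at mean 2.2 and less at mean 2.5; the simulation gives 0-4% across its wider SDs. Starters can be marked, but their number is not known. Third, the footnote does not touch the histology or EFS tests, alpha or power.

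**What to change.** 1. Derive an on-anticoagulant flag for each INR sample date from the coded, dated concomitant-medication records, using a pre-listed set of drugs and the partial-date conventions of SAP 7.4.2.
2. Replace the Appendix 2 footnote. For subjects anticoagulated at baseline, apply the printed baseline-multiple limits while the flag is on; otherwise use the absolute limits.
3. Present treatment-emergent, Grade 3-4 and marked INR abnormalities separately for values on and off anticoagulation. This separates new starters, whom step 2 does not regrade.
4. State in SAP 7.2.3 that its anticoagulation condition uses the same flag, since that section does not say where the status comes from.

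The cost is a small amount of programming and a merge with data already collected; no new data are needed. The downside is additional Grade 1-2 INR entries among stable users, because any rise above baseline is Grade 1 under the printed limits. The separate display keeps these apart from the off-anticoagulation rows. If the SAP is not revised, the change should be documented in the CSR, as SAP Section 1 requires.
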